### **3.5 Subset analyses**

The two co-primary endpoints and three efficacy secondary endpoints will be re-analyzed separately for (a) ages <60, [60, 70), and  $\geq 70$ , (b) men and women, (c) white and other, (d) Non-Hispanic and Hispanic.

### **3.6 Sensitivity analyses**

The two co-primary endpoints and three efficacy secondary endpoints will be re-analyzed separately in the per-protocol population to exclude treatment failures.

## **4. HYPOTHESES**

### **4.1 Primary Hypotheses**

The trial has co-primary hypotheses – requiring success on both for a successful trial. First, pain reduction must be demonstrated for Ampion vs. saline control. Next a function improvement must be shown on Ampion vs. saline control.

Reduction in Pain, as measured by a change in the WOMAC A pain subscore as measured by the 5-point Likert scale between Baseline and Week 12, will be greater in patients treated with Ampion than with saline:

$$\begin{array}{ll} \text{Null Hypothesis:} & \mu_A = \mu_S \\ \text{Alternate Hypothesis:} & \mu_A < \mu_S \end{array}$$

Where  $\mu_A$  = mean pain reduction in Ampion arm;  $\mu_S$  = mean pain reduction in saline arm. Lower mean change scores indicate greater pain reduction.

Improvement in function, as measured by a reduction in the WOMAC C function sub score as measured by the 5-point Likert scale between Baseline and Week 12, will be greater in patients treated with Ampion than with saline:

Null Hypothesis:  $\mu_A = \mu_S$   
Alternate Hypothesis:  $\mu_A < \mu_S$

Where  $\mu_A$  = mean function reduction in Ampion arm;  $\mu_S$  = mean function reduction in saline arm. Lower mean change scores indicate greater improvement in function.

## **5. DEFINITIONS**

### **5.1 Abbreviations**

Abbreviation	Definition
ATC	Anatomical Therapeutic Chemical Classification System
ITT	Intent to Treat Population
MedDRA®	Medical Dictionary for Regulatory Activities
mL	Milliliter
mmHg	Millimeters of mercury
MMRM	Mixed-effects model with repeated measures
NA	Not applicable
OA	Osteoarthritis
OARSI	Osteoarthritis Research Society International
OMERACT	Outcome Measures in Rheumatology
PGA	Patient's global assessment of disease severity
PP	Per protocol population
SAE	Serious adverse event
SAS	Statistical Software from SAS Institute
SD	Standard deviation
SEM	Standard error of the mean
TEAE	Treatment-emergent adverse event
WOMAC®	Western Ontario and McMaster Universities Arthritis Index

### **5.2 Definitions**

#### **Adverse Event (AE)**

An adverse event (AE) is defined as any undesired medical occurrence in a patient or clinical investigation patient receiving a pharmaceutical product and which does not necessarily have a causal relationship with this treatment. Therefore, an AE can be any unfavorable sign and unintended sign (including an abnormal laboratory finding),

symptom, or disease temporarily associated with the use of a study drug, whether or not related to the study drug.

AEs will be graded for severity using the following categories. Missing grade will be assigned a grade of 3 (severe) in tabulations:

**Grade 1 (MILD):** The symptom is barely noticeable to the study patient and does not influence performance or functioning. Concomitant medication is not ordinarily indicated for relief of mild AEs.

**Grade 2 (MODERATE):** The symptom is of sufficient severity to make the study patient uncomfortable and to influence performance of daily activities. Concomitant medication may be indicated for relief of moderate AEs.

**Grade 3 (SEVERE):** The symptom causes severe discomfort, sometimes of such severity that the study patient cannot continue in the study. Daily activities are significantly impaired or prevented by the symptom. Concomitant medication may be indicated for relief of severe AEs.

Relationship to study drug will be coded using the following categories. Missing relatedness will be assigned to 'Related' in tabulations:

**Unrelated:** The adverse event is unlikely to have been caused by study drug.

**Possibly related:** It is unclear whether the adverse event may have been caused by study drug.

**Related:** The adverse event is likely to have been caused by study drug.

Relationship to procedure will be coded using the following categories. Missing relatedness will be assigned to 'Related' in tabulations:

**Unrelated:** The adverse event is unlikely to have been caused by procedure.

**Possibly related:** It is unclear whether the adverse event may have been caused by procedure.

**Related:** The adverse event is likely to have been caused by procedure.

#### **Treatment-Emergent AE:**

A treatment-emergent AE (TEAE) is any AE that begins or increases in severity after the initial dose of study drug.

#### **Serious Adverse Event:**

A serious adverse event (SAE) is any untoward medical occurrence that occurs at any dose that:

- Results in death

- Is life-threatening (patient is at immediate risk of death from the event as it occurred)
- Requires in-patient hospitalization (formal admission to a hospital for medical reasons) or prolongation of existing hospitalization
- Results in persistent or significant disability/incapacity
- Results in a congenital anomaly/birth defect

Hospitalizations for elective surgery or other medical procedures that are not related to a treatment-emergent AE are not considered SAEs.

### **Age**

Patient's age is defined as its integer value in years at enrollment.

### **Baseline**

For any variable, unless otherwise defined, Baseline at Day 0, Visit 1. If data are not available from Visit 1, then the last measurement recorded prior to Day 0 will be selected from the screening period.

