5.1.2 Visit 0 (Day -6, telephone contact): Pre-Baseline Daily Assessments

The following procedures will be performed:

- Review requirements for daily collection of WOMAC A pain evaluation using both the 5-point Likert scale and the 100mm VAS scale
- Confirm Baseline visit date
- It is possible, depending on the Baseline visit date and successful completion of Screening criteria defined above, that the first Pre-Baseline Daily Assessment may occur during the Screening visit.

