5.1.9 Visit 7 (Week 10 ± 7 days, telephone contact)

The following procedures will be performed:

- Perform WOMAC and PGA evaluations of the study knee
- Record AEs
- Record concomitant medications
- Review rescue medication use

5.1.10 Visit 8 (Week 11 ± 7 days, telephone contact): Pre-Week 12 Daily Assessments

The following procedures will be performed:

- Review requirements for daily collection of WOMAC A pain scores using both the 5-point Likert scale and the 100mm VAS scale
- Confirm Week 12 visit date

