### **3. STUDY ENDPOINTS AND COVARIATES**

#### **3.1 Primary Endpoints**

The trial will test whether Ampion can produce a superior improvement in pain vs. saline control and a superior improvement in function vs. saline. This goal is achieved using two co-primary endpoints:

Change in the WOMAC A weekly pain sub score between Baseline and Week 12  
Change in WOMAC C physical function sub score between Baseline and Week 12

An average of the daily WOMAC A pain assessments will be used to calculate the weekly pain score, at baseline and at Week 12.

Mean 12-week change in the WOMAC A pain score will be compared between Ampion and saline control. Mean 12-week change in WOMAC C physical function score will be compared between Ampion and saline control.

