#### **3.2 Secondary Endpoints**

- Change in PGA between Baseline and Week 12
- Change in 100mm VAS Pain scale between Baseline and Week 12
- Use of rescue analgesia (amount of acetaminophen used between Baseline and Week 12)
- Incidence and severity of treatment-emergent adverse events (TEAEs)

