## 13. SCHEDULE OF ASSESSMENTS AND PROCEDURES

	Screening	Pre-Baseline (phone)	Baseline	24-hours (phone)	Week 2 (phone)	Week 4 (phone)	Week 6	Week 8 (phone)	Week 10 (phone)	Pre-Week 12 (phone)	Week 12	Week 24	Early Term.
Assessments & Procedures	Visit -1 Day-28 to 0	Visit 0 Day -6 to 0	Visit 1 Day 0	Visit 2 Day 1	Visit 3 Day 14 ± 7	Visit 4 Day 28 ± 7	Visit 5 Day 42 ± 7	Visit 6 Day 56 ± 7	Visit 7 Day 70 ± 7	Visit 8 Day 77 ± 7	Visit 9 Day 84 ± 7	Visit 10 Day 174 ± 7	
Informed Consent	X												
Inclusion/exclusion criteria	X		X										
Medical history/prior medications	X		X										
Concomitant medications	X		X	X	X	X	X	X		X	X	X	
Urine sample			X**								X		
Physical examination	X		X				X				X	X	X
Vital Signs	X		X				X				X	X	X
Randomization			X										
Review Diary Completion Instructions	X								X				
Phone Contact Daily Collection Reminder		X									X		
WOMAC A (Likert)	X	X*	X***		X	X	X	X	X	X*	X***	X	X
WOMAC A (VAS)	X	X*	X***							X*	X***		X
WOMAC B and C (Likert)	X		X		X	X	X	X			X	X	X
PGA	X		X		X	X	X	X			X	X	X
X-ray 	X												
Study treatment			X										
Dispense Rescue medication			X										
Review Rescue medication				X	X	X	X	X	X		X	X	X
Adverse Events			X	X	X	X	X	X	X		X	X	X

Visits are in clinic except for Day 1 and Weeks 2, 4, 8 and 10 when patients will be contacted by telephone

X-ray may be acquired at Screening to satisfy inclusion criteria, "Index knee must be symptomatic for greater than six months with a clinical diagnosis of OA and supported by radiological evidence (KL 4) that is not older than six months prior to the date of screening".

\*Patients will complete 7 daily pain score assessments up to and including the Baseline and Week 12 visits to allow calculation of WOMAC A weekly pain scores. The Screening and first Pre-Baseline daily pain score collection may occur on the same day, in office or at home, as appropriate.

\*\*Urine will only be collected at Baseline if necessary to conduct a pregnancy test; collection to occur as applicable

\*\*\*The WOMAC may occur in office or at home, and may serve as the 7th WOMAC Daily Pain collection

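### The derivation of the gatekept 100 mm VAS pain endpoint is inconsistent: the schedule and protocol 10.3.6 point to a diary-week mean, while the SAP default points to a single Day 0 baseline and leaves Week 12 unstated

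*SAP*

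**What the plan says.** **Collection.** Protocol 5.1.2 (Visit 0) calls for "daily collection of WOMAC A pain evaluation using both the 5-point Likert scale and the 100mm VAS scale", and protocol 5.1.10 (Visit 8) calls for "daily collection of WOMAC A pain scores using both the 5-point Likert scale and the 100mm VAS scale". The schedule of assessments (protocol Table 6.1, SAP 13) has a separate WOMAC A (VAS) row. That row carries the same footnote mark as the Likert row in both diary windows: "Patients will complete 7 daily pain score assessments up to and including the Baseline and Week 12 visits". The footnote gives the purpose as calculating weekly WOMAC A scores. A further footnote lets the visit assessment serve as the seventh daily score.

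**Endpoint.** SAP 3.2 lists "Change in 100mm VAS Pain scale between Baseline and Week 12" as a secondary endpoint. Under SAP 8.6.7 it is tested at one-sided 0.025 after PGA, and rescue analgesia is tested only if VAS succeeds.

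**Derivation.** SAP 3.1, under Primary Endpoints, says "An average of the daily WOMAC A pain assessments will be used to calculate the weekly pain score, at baseline and at Week 12". SAP 2.3 ties that average to the primary efficacy analysis. Protocol 10.3.6 averages all WOMAC A pain scores in each window and names no scale. SAP 5.2 supplies the fallback: "For any variable, unless otherwise defined, Baseline at Day 0, Visit 1".

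**Model.** SAP 8.6.2 analyses VAS with a repeated-measures model with compound symmetry, with treatment and Baseline PGA as fixed effects. Protocol 10.4.2 describes a similar model with the baseline value as the covariate.

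**The concern.** A gatekept test at a controlled alpha should have one derivation, fixed before unblinding. Here a programmer could defend at least three:

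- the visit reading at each time;
- the diary-week mean at each time;
- the daily scores entered as repeated measures. The planned model is a repeated-measures one without a Week term, although the schedule shows VAS after Baseline only in the Week 12 window and at early termination.

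These can give different estimates and p-values, and the result decides whether rescue analgesia is tested at all. If single readings were used, the endpoint would be noisier than the scheduled data allow. VAS and Likert pain would then differ in time frame as well as in scale, which makes the two harder to compare.

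The covariate is a second inconsistency in the same analysis. PGA is a different instrument, so adjusting for it does not adjust directly for where the patient started on the VAS.

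**Working it through.** **1. Count of scheduled scores.** Days -6 to 0 inclusive make 7, which reproduces the schedule's figure of 7 per window. Two windows give 7 + 7 = 14. The visit score may be the seventh, so the total stays at 14.

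**2. What each rule does to those scores.**

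| Source | Baseline VAS | Week 12 VAS |
|---|---|---|
| Schedule footnote on the VAS row | weekly score | weekly score |
| Protocol 10.3.6, WOMAC A rule (no scale named) | mean, days -6 to 0 | mean, seven days to the visit |
| Protocol 10.3.6 and 10.3.11.5, general baseline rule | last pre-treatment value | silent |
| SAP 2.3 and 3.1 | weekly mean, for the primary analysis | weekly mean, for the primary analysis |
| SAP 5.2 default | Day 0, Visit 1 value | silent |
| SAP 3.2 and 8.6.2 | not stated | not stated |

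The literal SAP default uses 1 of 7 baseline scores and leaves 6 unused. At Week 12 the count is undefined.

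**3. Size of the difference.** The documents give no VAS variance or correlation. Assumptions: day-to-day correlation ICC = 0.7, 0.8 or 0.9; correlation of 0.5 between a patient's true Baseline and Week 12 levels; equal variances, set to 1 for a single reading; complete diaries.

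- Variance of an n-day mean: v(n) = ICC + (1 - ICC)/n, so v(1) = 1.
- Baseline-to-Week 12 covariance: c = 0.5 × ICC.
- Residual variance after adjustment for baseline VAS, same n at both times: v(n) - c²/v(n).

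| ICC | v(7) | c | Residual, single readings | Residual, 7-day means | Variance ratio | SE ratio |
|---|---|---|---|---|---|---|
| 0.7 | 0.743 | 0.35 | 0.878 | 0.578 | 0.659 | 0.812 |
| 0.8 | 0.829 | 0.40 | 0.840 | 0.635 | 0.757 | 0.870 |
| 0.9 | 0.914 | 0.45 | 0.798 | 0.693 | 0.869 | 0.932 |

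Full diaries at both times therefore cut the SE by about 19%, 13% and 7%.

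**4. If only the baseline is a single reading.** With the Week 12 mean and a single baseline covariate, the residual variance is v(7) - c², that is 0.620, 0.669 and 0.712. Averaging the baseline as well brings these to 0.578, 0.635 and 0.693. The SE ratios are 0.965, 0.975 and 0.987, a gain of about 3.5%, 2.5% and 1.3%. Most of the possible gain therefore depends on the Week 12 value, the part on which the SAP is silent.

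**5. If baseline VAS is not the covariate.** SAP 8.6.2 names Baseline PGA. Leaving out any effect of PGA, the change-score variance is 2(v(n) - c):

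- ICC 0.7: 1.300 for single readings, 0.786 for means, ratio 0.604.
- ICC 0.9: 1.100 for single readings, 0.929 for means, ratio 0.844.

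The variance falls by 40% and 16%. The figures in step 3 thus belong to the model with baseline VAS as covariate, not to the SAP model as written.

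**The case against.** The best defence is that VAS is already defined otherwise, so the SAP 5.2 fallback never applies. The documents treat the VAS as one response format of WOMAC A pain. The VAS row of the schedule, in the SAP as well as the protocol, carries the footnote whose purpose is the weekly score. The averaging sentences in protocol 10.3.6 and SAP 3.1 name neither VAS nor Likert. This is a fair reading, and it means the documents do not clearly discard the diary.

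It does not settle the matter. SAP 3.1 sits under Primary Endpoints, SAP 2.3 assigns the average to the primary analysis, and the primary pain endpoint is the Likert score. The secondary endpoint is named as a VAS pain scale, not as WOMAC A. If protocol 10.3.6 does cover VAS, it conflicts with the literal SAP default.

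A reader might infer that the SAP throws away 12 of the 14 scheduled VAS scores. The documents do not support that as a statement of the plan. The default concerns Baseline only, and no sentence makes the Week 12 VAS a single visit reading. The figure of 12 (14 - 2) holds only if a single reading is also used at Week 12.

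It is also fair to say that the documents show no bias between arms and no Type I error inflation from either derivation once it is fixed in advance, and that VAS is tested only after both co-primaries and PGA succeed. That limits the importance of the point.

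**Conclusion.** The point holds as an inconsistency in the definition of a gatekept endpoint. Seven daily VAS scores per window are scheduled, some passages point to their mean, and the SAP's literal default points to one Day 0 reading, with 6 of 7 baseline scores unused. Week 12 is unspecified, and the covariate differs between SAP 8.6.2 and protocol 10.4.2.

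The gain in precision rests wholly on assumed correlations. Single readings at both times against full diaries is the widest contrast: an SE reduction of about 19% to 7% with baseline VAS as covariate. Missing diary days would make it smaller. If only the baseline is a single reading, the difference is about 3.5% to 1.3%.

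A reader might go on to infer a stated loss of power for VAS. None can be computed, because the documents give no VAS effect size or SD; the 0.21 difference (0.83 - 0.62) and SD of 0.85 in the sample-size section are for Likert pain. The co-primary endpoints are unaffected. This should be corrected before unblinding, but it does not threaten the primary conclusion.

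**What to change.** In SAP 3.2, 5.2 and 8.6.2 and protocol 10.4.2, define the VAS endpoint as the change from the mean of the daily VAS scores in the Baseline diary week (before injection) to the mean in the Week 12 diary week, on the same days as the Likert weekly score. In SAP 8.6.2, replace Baseline PGA with that baseline VAS mean as the covariate, in line with protocol 10.4.2.

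Two details belong in the same edit. First, state the baseline window once: protocol 10.3.6 gives days -6 to 0 (7 days), while protocol 10.3.11.5 gives days -7 to 0 (8 days). Second, with one Week 12 value per patient the model reduces to a baseline-adjusted comparison, so the repeated-measures wording should say so, or say which repeated values are meant.

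The cost is wording and programming; the scores are already scheduled for collection. Protocol 10.3.10 foresees a final SAP before unblinding at the interim analysis, which is the natural place for the change.

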#### **Change from Baseline:**

The arithmetic difference between a post-Baseline value and the Baseline value:

Change from Baseline = (Post-Baseline Value – Baseline Value)

Percentage Change from Baseline = [(Post-Baseline Value – Baseline Value) / Baseline Value] x 100

### **End of Study**

End of study is at Visit 10 (Week 24), unless terminated early.

### **Enrollment date**

Enrollment date is the same as the randomization date and is designated Day 0.

### **Study drug**

Study drug in this study is 4 mL Ampion injection or 4mL saline.

### **Randomization date**

Randomization date is the day the patient is assigned a randomization number on study Day 0.

### **Study Day 0**

Day 0 is defined as the first day that study drug is administered to the patient.

### **Study Day**

Day of treatment: study day = (visit date - date of Study Day 0).

## **Treatment failure**

Treatment failures are defined as patients who receive additional medications or surgical procedures in order to treat worsened symptoms in the treated knee during the study; specifically, treatment failures are any patients who:

- Increase their corticosteroid dose of  $\leq 10$  mg above their starting dose of corticosteroid during the study to treat worsened symptoms in the treated knee;
- Increase use of NSAID pain medications by a clinically significant amount during the study to treat worsened symptoms in the treated knee;
- Begin opioid treatment during the study to treat worsened symptoms in the treated knee;
- Receive intra-articular injection of pain medicine in the treated knee during the study to treat worsened symptoms in the treated knee;
- Undergo total knee replacement or other surgical procedure in the treated knee prior to assessment of the primary efficacy endpoint.

## **6. ANALYSIS SUBSETS**

### **6.1 Data Subsets**

#### **6.1.1 Safety Analysis Set**

The safety analysis population is defined as all patients who are randomized and receive study medication (Ampion or saline). Patients will be analyzed as treated. Summaries of data will include all collected data.

#### **6.1.2 Intent to Treat (ITT) Analysis Set**

The intent-to-treat (ITT) analysis population is defined as all patients who are randomized. All efficacy analyses will be performed in the ITT population. Patients will be analyzed as randomized.

The ITT analysis set is the primary effectiveness analysis population. For the primary effectiveness analysis at Week 12, multiple imputation will be used to assign a value to those cases with missing data. The full conditional specification method with predictive means matching as described in Berglund & Heeringa (2014) will be used. This method uses all of an individual's known primary outcome measures at Baseline, 2, 4, 6, 8, 10, and/or 12 weeks to impute any missing values.

#### **6.1.3 Per Protocol (PP) Analysis Set**

The per protocol (PP) analysis population is defined as all patients who met all entry criteria and had no major protocol violations. All efficacy analyses will be repeated in the PP population. These analyses will be supportive of the ITT analysis. Patients will be analyzed as treated. No imputations will be performed.

## **7. INTERIM ANALYSIS AND EARLY STOPPING GUIDELINES**

There will be one interim analysis once 724 subjects have reached final assessment at Week 12.

At the interim analysis, the conditional probability based upon the observed treatment effect on the WOMAC C function score will be calculated. The minimal conditional probability that allows a sample size increase without inflating Type I error under the promising zone for a sample size increase up to 150% is 0.391. Any conditional power  $< 0.391$  results in going to 1,034 patients, randomized 1:1 for Ampion and saline IA injection. Sample size re-estimation according to the promising zone is done for conditional powers between 0.391 and 0.90 with a sample size increase capped to 1,552 total patients, randomized 1:1 for Ampion and saline IA injection.

The final analysis, defined by a sample size established using the promising zone, will use the critical value with one-sided  $\alpha = 0.025$  for WOMAC A (Ampion vs. saline control) and WOMAC C (Ampion vs. saline control).

## **7.1 Data Handling and Electronic Transfer of Data**

See Data Management Plan (DMP).

## **7.2 Handling of Missing and Incomplete Data**

All data collected under this study protocol will be included in the assessment of patient safety. Missing or incomplete AE data will assume greatest relationship to study drug and/or severity. Incomplete adverse event and concomitant medication dates will be imputed as described in Section 12. If imputed dates are used, then they will be identified as such in the final study report. If an AE start date is missing or partially missing and no additional information is available from the site in order to establish whether the event started before or after the dose of study drug, the event will be considered to have started after dose. Partially missing dates where the month and year is prior to Day 0 will be classified as pre-dose.

For the co-primary effectiveness analysis of WOMAC pain change and WOMAC C function change, missing change scores will be imputed when the ITT analysis population is used. Missing data will be imputed by the fully conditional specification predictive mean matching multiple imputation approach of Berglund and Heeringa (2014). A sensitivity analysis will be conducted in which the missing 12-week endpoint is replaced by the Baseline WOMAC pain score.

For the secondary endpoints of PGA, 100mm VAS, and number of acetaminophen pills used, missing values will be imputed when the ITT analysis population is used. Imputation methods employed will be multiple imputation (SAS PROC MI and SAS PROC MIANALYZE) and single imputation methods (i.e., regression-based estimates, Baseline imputation, LOCF, and a worst/best case imputation).

Per the WOMAC User Guide, the patient's response will be regarded as invalid, and the subscale(s) deficient, in the event that two pain, both stiffness, or more than four physical function items are omitted. Further, if one pain, one stiffness, or 1-3 physical function units

are missing, the average value for the subscale will be substituted in lieu of the missing item value(s).

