5.1.13 Early Termination Visit

The following procedures will be performed at Early Termination Visit:

- Perform and record physical examination
- Record vital signs. (Measure body temperature, SBP, DBP and pulse rate)
- Perform WOMAC and PGA evaluations of the study knee using both the 5-point Likert scale and the 100mm VAS scale
- Record AEs
- Record concomitant medications
- Review rescue medication use

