10.3.6 Definition of Study Visits

This clinical trial has a total of 11 study visits, including telephone contacts, during the 24-week study (see Table 6.1). The time-on-study for each patient observation will be defined relative to Day 0, the day of the initial dose. For analysis, the Baseline measure is the latest measure prior to initiation of treatment. For analysis of Baseline WOMAC A pain, the Baseline pain score is the average of all scores measured during days -6 to 0, prior to injection of treatment. For analysis of Week 12 WOMAC A pain, the Week 12 pain score is the average of all scores measured during the seven days prior to and including the Week 12 office visit.

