### **8.6 Efficacy Analyses**

All efficacy variables will be assessed at Baseline (Day 0), Week 2, Week 4, Week 6, Week 8, Week 10, Week 12, and Week 24. Differences between treatments (Ampion and saline arms) will be presented using mean differences and 95% confidence intervals. Endpoints will be compared between Ampion and saline.

For summaries based on the PP, missing data will not be estimated or carried forward in any of the descriptive analyses. For summaries based on the ITT population, estimates from the MMRM will be shown incorporating imputed missing data via the full conditional specification method with predictive mean matching.

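### SAP 7.2 should name the predictors for imputing Week 12 VAS: before the Week 12 diary, VAS is taken after Baseline only at Early Termination, while Likert pain is scored at five visits

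*SAP*

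**What the plan says.** **Endpoint.** SAP 3.2 lists "Change in 100mm VAS Pain scale between Baseline and Week 12". Under SAP 8.6.7 it is tested at one-sided 0.025, only after both co-primaries and PGA succeed, and it in turn gates rescue analgesia.

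**Imputation of the secondaries.** SAP 7.2 gives one list for PGA, VAS and pill count together. It starts with multiple imputation, run in PROC MI and PROC MIANALYZE. The rest of the list is "single imputation methods (i.e., regression-based estimates, Baseline imputation, LOCF, and a worst/best case imputation". It does not say which method is primary, which variables enter the models, or whether an Early Termination value feeds LOCF.

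**Imputation of the co-primaries.** Here the predictors are given. SAP 6.1.2 says of missing values: "This method uses all of an individual's known primary outcome measures at Baseline, 2, 4, 6, 8, 10, and/or 12 weeks to impute any missing". SAP 8.6.1 repeats this.

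**When VAS is collected.** Protocol Table 6.1 and the SAP section 13 schedule mark WOMAC A (VAS) at Screening, Pre-Baseline, Baseline, Pre-Week 12, Week 12 and Early Termination. Weeks 2, 4, 6, 8, 10 and 24 are blank. The visit text agrees. Protocol 5.1.10 (the Week 11 call) says "Review requirements for daily collection of WOMAC A pain scores using both the 5-point Likert scale and the 100mm VAS scale", and Protocol 5.1.13 (Early Termination) says "Perform WOMAC and PGA evaluations of the study knee using both the 5-point Likert scale and the 100mm VAS scale".

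**The statement that does not fit.** SAP 8.6: "All efficacy variables will be assessed at Baseline (Day 0), Week 2, Week 4, Week 6, Week 8, Week 10, Week 12, and Week 24".

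**The concern.** The listed methods read as if each endpoint had a series of values after Baseline. VAS has almost none before the Week 12 diary. Two consequences follow for a patient with no Early Termination VAS and no Week 12 diary day:

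- LOCF returns the Baseline value, so two of the listed analyses are the same analysis.
- A model built on the pattern set for the co-primaries (the outcome's own history) has only pre-treatment VAS to work from. If the patient left because pain returned, that model gives them roughly the improvement of patients who stayed and had a similar Baseline.

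The analysis model cannot make up for this. SAP 8.6.2 calls it an MMRM, but with one post-Baseline time point it borrows nothing from interim visits. Imputation is therefore the only route by which interim pain can inform a missing Week 12 VAS. At stake are the estimate for a gated secondary endpoint, and the freedom to choose among unranked methods after unblinding. The co-primaries are not affected.

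**Working it through.** **1. Scheduled values.**

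| Occasion | Likert WOMAC A | 100 mm VAS |
|---|---|---|
| Baseline (diary and visit) | yes | yes |
| Weeks 2, 4, 6, 8, 10 | 5 values | 0 values |
| Week 12 (diary and visit) | yes | yes |
| Early Termination | yes | yes |

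**2. What LOCF returns for VAS.**
- Early Termination visit attended: the VAS taken there.
- No such visit, but some Week 12 diary days: possibly no imputation at all. Protocol 10.3.6 says of WOMAC A pain that "the Week 12 pain score is the average of all scores measured during the seven days prior to and including the Week 12 office visit". If that rule also covers VAS, a partial diary gives a score.
- Neither: the Baseline value, identical to Baseline imputation.

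**3. How many patients.** The plan enrols 1,034 to obtain 984 at 5% dropout. Its figure is reproduced by 984 × 1.05 = 1,033.2, rounded up to 1,034 (984 / 0.95 would give 1,036). The number without a Week 12 value is then about 1,034 − 984 = 50, or 0.05 × 1,034 ≈ 52. The subset with no Early Termination VAS and no diary day is smaller and cannot be derived from the documents.

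**4. Scale of the effect.** No VAS effect or SD is given. The planned Likert effect is 0.83 − 0.62 = 0.21 with SD 0.85, or 0.21 / 0.85 = 0.25 SD. Rescaling 0–4 to 0–100 mm (an assumption) gives 0.21 / 4 × 100 ≈ 5.3 mm and 0.85 / 4 × 100 ≈ 21 mm.

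**5. What the interim Likert scores add.** The documents give no correlations, so these are assumed: Baseline VAS with Week 12 VAS, 0.3 to 0.5; each interim Likert score with Week 12 VAS, 0.5 to 0.7. Baseline VAS alone then explains 9% to 25% of the variance of Week 12 VAS (0.3² to 0.5²). With five Likert scores, assumed to correlate 0.6 to 0.75 with each other, this rises to 38% to 62%.

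**6. Bias in closed form.** Suppose that in one arm a fraction f is missing, and that those patients differ by g SD on the last Likert score, given Baseline. Baseline-only imputation then shifts the treatment difference by f × b × g. Here b = (r_L − r_B × r_BL) / (1 − r_BL²) is the slope on Likert given Baseline.
- Low end: b = (0.5 − 0.3 × 0.3) / (1 − 0.09) = 0.45. With f = 0.05 and g = 0.25, the shift is 0.006 SD.
- High end: b = (0.7 − 0.5 × 0.5) / (1 − 0.25) = 0.60. With f = 0.05 and g = 1.0, the shift is 0.030 SD.
- At f = 0.20 the range is 0.023 to 0.12 SD.

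Against 0.25 SD, the 5% range is roughly 2% to 12% of the effect.

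**7. Simulation.** 1,500 trials, 517 per arm, 4% to 5% missing, with logistic dropout on Week 8 Likert change (slope 1.5 per point). The slope and the VAS–Likert correlation are assumptions.

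| Who drops out | Full data (mm) | Baseline-only | Baseline + Week 8 Likert | Shift, Baseline-only |
|---|---|---|---|---|
| Same rule, both arms | -5.27 | -5.11 | -5.26 | -3% |
| Ampion only | -5.24 | -5.72 | -5.24 | +9% |
| Saline only | -5.31 | -4.69 | -5.31 | -12% |

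A second simulation, with residual VAS–Likert correlation 0.5 to 0.7, gave -4% to -6% with the same rule in both arms and about 9% missing. With one-arm dropout at 4% to 5% missing overall, it gave +15% to +20% (Ampion only) and -19% to -26% (saline only). The direction is the same, but the size depends on the assumptions.

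**8. Against sampling error.** With SD 21.25 mm, the standard error is 21.25 × √(2/517) = 1.32 mm. The three shifts in the table (0.16, 0.48 and 0.62 mm) are 0.12, 0.36 and 0.47 standard errors.

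**The case against.** A reader might infer that LOCF has nothing to carry for VAS, or that the SAP's imputation is blind to interim pain. The documents support neither reading.

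- Early Termination includes a VAS, and it is taken in just the patients for whom LOCF matters.
- SAP 7.2 names no predictors, so the Likert scores are not excluded. The wording about an individual's prior data is in SAP 8.6.1 and concerns the co-primaries. SAP 8.6 also mentions the fully conditional specification method for ITT summaries.

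Both points stand, and they limit this to under-specification.

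Three further points stand in part:

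- The list serves three endpoints, and LOCF does have interim values for PGA. Where LOCF equals Baseline imputation it assigns no improvement, so the duplication is redundant but does not flatter the drug. The risk lies in the model-based methods.
- In the simulation, Week 8 Likert drives dropout and is then added to the model. That the bias vanishes follows by construction, and it needs Week 8 to be observed. Patients who leave earlier supply fewer scores, and dropout that depends on unrecorded pain would not be fully corrected.
- The larger shifts need dropout in one arm only, which is a bounding case.

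The sentence in SAP 8.6 is generic, and the VAS-specific text and schedule are clear enough to override it. It should still be made to agree with them.

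**Conclusion.** The point holds as a free improvement to an under-specified part of the SAP, not as a proven error. Three facts rest on the documents alone: no VAS is scheduled at Weeks 2 to 10; LOCF equals Baseline imputation for patients with neither an Early Termination VAS nor a Week 12 diary day; and SAP 8.6 disagrees with the schedule.

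The size rests on assumed correlations, an assumed dropout slope and a rescaled Likert effect. At the planned dropout with the same rule in both arms, the shift is about -3% of the effect, towards no difference and about 0.12 standard errors. It grows if dropout differs by arm or exceeds 5%.

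It would be wrong to infer that the VAS result is invalid or that trial success is at risk. VAS is a gated secondary endpoint and the co-primary imputation already uses Weeks 2 to 10.

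**What to change.** Before unblinding, amend the SAP as follows.

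1. **SAP 7.2, primary method.** Impute Week 12 VAS by multiple imputation with the fully conditional specification method. Predictors: Baseline VAS, treatment arm, Likert WOMAC A at Baseline and Weeks 2, 4, 6, 8, 10 and 12 where observed, and any Early Termination VAS.
2. **SAP 7.2, Early Termination.** State how that VAS enters the model. Patients who leave before Week 12 will seldom have both an Early Termination and a Week 12 VAS, so the data can hardly estimate its coefficient as an ordinary column. The Likert score from the same visit can be allocated to the nearest scheduled week, where other patients supply the relation. Also say whether the partial-diary averaging rule covers VAS.
3. **SAP 7.2, LOCF.** Keep it for VAS only as a sensitivity analysis that carries an Early Termination VAS, and note that it otherwise equals Baseline imputation.
4. **SAP 8.6.** Reconcile with the schedule: VAS at Screening, Baseline with its diary, the Week 12 diary and visit, and Early Termination.

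In the same edit, reconcile the VAS covariate: SAP 8.6.2 adjusts for Baseline PGA, whereas Protocol 10.4.2 adjusts for the Baseline value.

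The cost is SAP wording and a few more variables in the imputation program. All the data are already scheduled for collection.
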